6.1.3. Accrual Objectives

The study plan is to accrue 60 patients. It is anticipated that most recurrent low-grade glioma patients completing surgical resection will be eligible for enrollment and will choose to participate. Based on current patient volume in the UCSF neurologic-oncology clinic, it is expected that a minimum of 3 patients per month will be enrolled.

6.1.3. Estimated Duration of Study

With enrollment of 3 patients per month, accrual can be completed in a 20 month period. With up to an additional 6 months of treatment to assess best response for the last accrued patient, the approximate duration of study is 26 months.

Based on review of UCSF historical data, we expect approximately one-third of recurrent low-grade glioma patients to present with high-grade gliomas. Therefore, we should be able to complete enrollment of 40 low-grade glioma patients and 20

secondary malignant glioma patients at approximately the same time. In order to evaluate our primary objective, enrollment will continue until at least 40 low-grade glioma patients have enrolled.

6.1.4 Analyses Time-points and planned analysis

Primary end-point – 6-month PFS:

Analyses will be performed after all enrolled patients have completed 6 months on study drug, or whenever the progression status of all patients has been established, whichever comes first. The primary analysis will be based on Kaplan-Meier method. Kaplan-Meier estimates and the associated 95% CIs will be calculated for the 6-month PFS separately for low-grade glioma patients and secondary malignant glioma patients. The Cox proportional hazards model will also be used to allow for adjustment of the prognostic factors including age, KPS, extent of resection, and number of prior chemotherapy regimens.

Secondary end-point – overall survival and objective response rate:

The method described above for the analysis of PFS-6 will be applied to the analysis of OS. Response is based on the best response, defined as the best objective status as measured by the sum of products of perpendicular diameters of all measurable lesions. The point estimate and the associated 2-sided 95% CI for the response rate will be calculated separately for low grade and secondary malignant tumors.

Secondary end-point – biologic correlates:

The endpoints of overall survival, objective response rate and progression status at 6 months will be evaluated for impact of phosphorylated PKB/Akt status. We anticipate that the response rate may be more dependent on phosphorylated PKB/Akt status than on current tumor grade. We also expect approximately 50% of the low-grade tumors to be phosphorylated PKB/Akt positive and 75% of the higher-grade tumors to be positive. This will result in approximately 20 phosphorylated PKB/Akt positive low-grade cases and 15 phosphorylated PKB/Akt positive high-grade cases for secondary analyses. A consideration of phosphorylated PKB/Akt status as a predictor of response will use the Cochran Mantel-Haenzel test stratified by grade. If the number of responses is sufficient, logistic regression will be used to evaluate the potential impact of phosphorylated PKB/Akt status on the likelihood of response adjusting for grade. Estimates of the odds ratio and its associated 95% confidence interval will be calculated to determine if future studies of RAD001 should require prior assessment of phosphorylated PKB/Akt status. The same methods will be used to determine if phosphorylated PKB/Akt status predicts progression status at 6 months stratified by grade. The impact of phosphorylated PKB/Akt status on OS will be assessed using the proportional hazards models adjusting for grade. Estimates of the hazard ratio and its associated 95% confidence interval will be calculated. We will repeat these analyses on patients based on PTEN promoter methylation status.

Exploratory analysis – radiographic responses:

We will determine if the pretreatment imaging and changes from pre-treatment to first post-treatment scan correlate with the clinical endpoints of time to tumor progression and survival. A scoring system will be developed for predicting outcome based on the initial, pretreatment scan. Since all of these patients will have surgery, it will be possible to prospectively determine if the imaging score can predict grade as assessed by the neuropathologist. However, since most patients do not have surgery at time of progression, and time to progression varies even among those with the same tumor grade, we want to determine how useful this score will be beyond the current histology information. We plan to test the usefulness of this score in predicting PFS and survival using Cox regression. If the number of patients with responses is sufficient we will also assess the ability of the imaging score to predict response using logistic regression. The models will include, in addition to the imaging score, age, KPS, extent of resection, time since diagnosis, and initial diagnostic histology scored as oligodendrogloma only vs. those with an astrocytoma component. Because PKB/Akt phosphorylation status is predicted to impact outcome for this particular therapy, this will also be included in the model. The inclusion of these additional variables is to adjust for known or potential confounding risk factors. The primary hypothesis test will focus on the ability of the prediction score to add information beyond what would have been known based on the clinical data.

The patients will initially be categorized as predicted upgraded (Yes/No) consistent with the primary question posed. For supplementary analyses the prediction score will be included as a continuous variable, or we may create a score – based, for example, on the quartiles of the values observed in the previously studied cases – to determine if a further refinement in prediction of outcome can be achieved. A further analysis will include the known current histologic grade to determine if the score provides information even adjusted for this variable. Based on preliminary data we expect 1/3 of low-grade patients to be upgraded to high-grade glioma on recurrence. If we make the assumption that the predicted distribution will be the same, then we will be comparing 20 predicted high grade vs. 40 predicted low grade patients for the overall assessment. Because these patients are being treated at time of progression, we anticipate that we will know the progression time for most of them at the time of the analysis. Assume that the analysis is done when 50 of the 60 event times are known and $\alpha=0.05$ one-tailed. There would be over 80% power to detect the difference if the hazard ratio was 2.2.

The analysis of the change from initial to first post treatment scan will be performed in a similar manner except that there will be the additional covariate of baseline prediction score, since we will want to know if the change from baseline adds information beyond what was available at the initial scan. The primary endpoints will be

PFS and survival. Fewer patients will be available for this assessment since some will progress at the time of their first post treatment scan. The power for testing hypotheses within this clinical trial is limited by the number of patients enrolled on the trial. We plan to estimate hazard ratios together with confidence intervals to determine if the MR parameters continue to look promising in this treatment group.

7 References

Bjornsti MA and Houghton PJ (2004) The TOR pathway. A target for cancer chemotherapy. *Nat Rev Cancer*; 4:335-338.

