6.1 Statistical methods

6.1.1. Stopping Rules

If the discontinuation rate due to toxicity is 20% or greater and the lower bound for the one-tailed 95% confidence interval is $> 10\%$, this strategy would not be considered feasible. At the time we observe any toxicity that requires permanent discontinuation of drug, we will estimate, with confidence intervals, the rate of toxicity. If there is a greater than 20% rate for discontinuation of drug during therapy the study will stop and we will assess the study design. Because the confidence interval may be calculated multiple times, the actual confidence level will be overstated. This increases the likelihood of rejecting the therapy due to toxicity. However, this is felt to be an acceptable risk in order to prevent continuation of a therapy that may have a toxicity rate that precludes its routine use.

If there is any treatment related mortality event, the study accrual will be suspended until all data pertaining to the event is reviewed by the Study Chair and co-investigators.

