6.1.2. Endpoint Definitions and Sample Size

The following definitions will be used for statistical analysis:

- Response: Response is based on the best response. The best response is defined as the best objective status as measured by the sum of products of perpendicular diameters of all measurable lesions.
- Progression-free survival: Number of days from the day the patient was enrolled to the day the patient experiences an event of disease progression or recurrence or to the date of death if disease progression or recurrence is not reached. All events of disease progression or recurrence will be included, regardless of whether the event

occurred while the patient was still taking drug or had previously discontinued study drug. All events of death will be included for patients who had not experienced disease progression or recurrence. If the patient does not have an event of disease progression or recurrence nor as the patient died, the patient's data will be censored at the date of last contact with the patient.

- Overall survival: Number of days from the day the patient was enrolled until the date of death. If the patient is lost to follow-up, the patient's data will be censored at the date of last contact with the patient.

For this single-arm phase II trial, the primary endpoint will be 6-month progression-free survival (PFS-6). Patients will be analyzed based on intention to treat. The primary determination of treatment success will be based on the results for those patients who are shown to still be low-grade. The intent is to perform the primary analysis at the time the 6 month PFS is known for all patients.

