Precise documentation of prognosis among recurrent low grade glioma patients treated with targeted therapy is limited in literature. A recent study based on the experience of the North American Brain Tumor Consortium (NABTC) was conducted to assess whether progression status at 6 months predicts survival from that time among recurrent high-grade glioma adult patients (Lamborn, Yung et al. 2008). In that study, it was reported that the estimated PFS-6 among recurrent grade III glioma patients who were not treated with temozolomide, a chemotherapy which is part of the standard of care for newly diagnosed gliomas, is approximately 17%. Since we expect patients with recurrent low grade gliomas to have better prognosis than grade III patients, we consider the lower threshold for the probability of 6-month PFS to be 17%. The calculation of sample size is based on a binary endpoint with the goal to increase 6-month PFS rate to 40%. This translates into a hazard ratio of 0.52 (experimental/historical). 40 patients will provide over 90% power using a one-sided test with alpha of 0.05.

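### Does the plan lack a success rule for 6-month PFS because Section 6.1.4 lists only a Kaplan-Meier estimate with a 95% CI?

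*Combined protocol and SAP*

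**What the plan says.** Section 6.1.2 (Endpoint Definitions and Sample Size) sets out the hypothesis. On the null: "we consider the lower threshold for the probability of 6-month PFS to be 17" per cent. On the target and the type of endpoint: "The calculation of sample size is based on a binary endpoint with the goal to increase 6-month PFS rate to 40" per cent. On size: "40 patients will provide over 90% power using a one-sided test with alpha of 0.05". On who decides the result: "The primary determination of treatment success will be based on the results for those patients who are shown to still be low-grade". The same section specifies intention-to-treat analysis, counts progression whether or not the patient is still on drug, and intends the primary analysis for when every patient's 6-month status is known.

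Section 6.1.4 (Analyses Time-points and planned analysis) then gives the method: "The primary analysis will be based on Kaplan-Meier method. Kaplan-Meier estimates and the associated 95% CIs will be calculated for the 6-month PFS". The two tumour groups are analysed apart, and a Cox model adjusts for prognostic factors. The section does not mention 17%, a one-sided test or alpha. It does not say whether the PFS interval is one- or two-sided, although it labels the response-rate interval as two-sided.

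Two other places bear on the point. Section 6.1.1 (Stopping Rules) frames its toxicity criterion with a labelled bound: "the lower bound for the one-tailed 95% confidence interval is" above 10%. Section 6.1.3 (Estimated Duration of Study) makes 40 a minimum: "enrollment will continue until at least 40 low-grade glioma patients have enrolled".

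**The concern.** The trial was sized for a one-sided 5% test of a fixed rate, and the plan promises a determination of success. Yet the section that describes the analysis contains only an estimate and an interval. The Cox model cannot fill the gap, because a single-arm Cox model does not test whether a 6-month rate exceeds 17%.

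If the interval were used as the criterion, its sidedness and formula would matter, and Section 6.1.4 fixes neither. At 40 patients, neighbouring cut-offs have visibly different properties. A cut-off of 11 has a type I error above the planned 5%, and a cut-off of 13 has power below the stated 90%. A borderline result could then be called after the data are seen, which a single-arm trial with one primary endpoint should avoid.

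**Working it through.** **Inputs.** n = 40 low-grade patients, null p0 = 0.17, target p1 = 0.40, one-sided alpha 0.05, binary endpoint (all from Section 6.1.2). The counts below assume exactly 40 patients and no censoring before 6 months, so the Kaplan-Meier estimate equals r/40.

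**Step 1: reproduce the plan's figures.** The hazard ratio is ln(0.40)/ln(0.17) = (−0.916)/(−1.772) = 0.517, which matches "This translates into a hazard ratio of 0.52 (experimental/historical". For the exact binomial test, find the smallest r with P(X ≥ r | 40, 0.17) ≤ 0.05:

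| Cut-off r | Type I error, P(X ≥ r \| 0.17) | Power, P(X ≥ r \| 0.40) |
|---|---|---|
| 11 | 6.6% | 96.5% |
| 12 | 3.0% | 92.9% |
| 13 | 1.2% | 87.1% |

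The answer is r = 12, with power 92.9%. The normal approximation gives 95.6%. Both agree with the plan's over 90%.

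**Step 2: suppose a two-sided 95% interval were the criterion** (lower limit above 0.17). At 12/40, S = 0.30 and the standard error is √(0.30 × 0.70/40) = 0.0725.

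- Plain: 0.30 − 1.96 × 0.0725 = 0.158, which fails.
- Log-log: the standard error is √(0.70/12)/|ln 0.30| = 0.2006, and the limit is 0.30^exp(1.96 × 0.2006) = 0.168, which fails.
- Log: the standard error is √(0.70/12) = 0.2415, and the limit is 0.30 × exp(−1.96 × 0.2415) = 0.187, which passes.
- Exact binomial gives 0.166 (fails). Logit gives 0.179 and Wilson 0.181 (both pass).

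At 13/40 all of these exceed 0.17 (plain 0.180, log-log 0.188, exact 0.186, for example). At 11/40 all fall below it (the highest is log, 0.166). So the two-sided reading gives 12 or 13, and only exactly 12 of 40 is in dispute:

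- at a true rate of 40%, P(X = 12) = 92.9% − 87.1% = 5.8%;
- at a true rate of 17%, P(X = 12) = 3.0% − 1.2% = 1.8%.

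**Step 3: can 11 of 40 count as success?** Only if the unlabelled 95% CI is read as a one-sided bound and log (0.180), logit (0.175), Wilson (0.176) or Jeffreys (0.173) limits are used. The one-sided plain (0.159), exact (0.163) and log-log (0.167) bounds all reject it. A cut-off of 11 has a type I error of 6.6%, which the alpha of 0.05 in Section 6.1.2 rules out.

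**Step 4: more than 40 patients.** The exact one-sided 5% test adapts by itself. The cut-off is 12 for n = 40 to 42 and 13 for n = 43 to 47. The type I error stays between 2.3% and 4.6%, and power is at least 92.9% throughout.

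**Step 5: would writing in a Kaplan-Meier bound do better?** Take a one-sided 95% log-log bound above 17%. It gives the same cut-off of 12 at n = 40. At n = 43 it accepts 12, with exact type I error 5.08%, and at n = 48 it accepts 13, with 5.37%. The exact test would require 13 and 14 there. The substitute is therefore slightly worse at holding 5% than the test Section 6.1.2 already implies.

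**The case for a change.** The strongest reply is that Section 6.1.2 describes a sample-size calculation, not an analysis. Section 6.1.4 names Kaplan-Meier, with censoring at last contact, as the primary method. A binomial count is not defined for a patient lost before 6 months, so on this view the sizing test cannot simply be carried over. It is also true that no sentence anywhere states the rule, although the plan is more explicit about intervals for toxicity and for response.

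Part of this stands: the rule has to be inferred, and one sentence in Section 6.1.4 would have removed the question. The rest carries less weight. The plan intends to analyse once every patient's 6-month status is known, and it counts progression after drug is stopped, so early censoring should be rare. With none, the Kaplan-Meier estimate is r/n and the two methods coincide. Some loss changes little. The documents give no dropout rate, so I assumed 5% or 10% loss by 6 months with exponential event times. In simulation, a one-sided 95% log-log Kaplan-Meier bound against 17% then has about 93% to 94% power and a type I error of about 4%.

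The contrast with the toxicity rule is also weaker than it looks. Section 6.1.1 names no interval method either. And because it says one-tailed where it means one-tailed, an unlabelled 95% CI is naturally read as two-sided and descriptive.

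**Conclusion.** The concern does not call for a change. Section 6.1.2 fixes the null, the target, the sidedness, the alpha, the endpoint type and the deciding population. Together these give one exact rule at 40 patients: at least 12 progression-free at 6 months, type I error 3.0%, power 92.9%. The Kaplan-Meier estimate and its 95% CI report the size of the effect and need not replace that test. No rule the plan states produces a wrong result, and the sample size and power are correct.

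The most that could go wrong is that someone uses a two-sided 95% CI as the criterion with plain, log-log or exact limits. Power would then be 87.1% rather than 92.9%, and the conclusion would differ only at exactly 12 of 40 (probability 5.8% at a 40% rate, 1.8% at 17%). That error is conservative, since it makes success harder to declare. These figures assume 40 low-grade patients with complete 6-month status. With more patients, the same exact test at the actual number holds 5%.

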Everolimus was also shown to have activity in human pancreatic neuroendocrine cells, where induction of apoptosis was reported (Zitzmann, et al 2007), as well as in acute myeloid leukemia cells (Zeng, et al 2007), mantle cell lymphoma cells (Haritunians, et al 2007), adult T-cell leukemia cells (Ikezoe, et al 2007), diffuse large B cell lymphoma cells (Wanner, et al 2006), pancreatic tumor cells (Tuncyurek, et al 2007), ovarian cancer cells (Treeck, et al 2006, Mabuchi, et al 2007) and hepatocellular carcinoma cells (Sieghart, et al 2007). Everolimus was also evaluated in a clonogenic assay using cells derived from 81 patient derived tumor xenografts never cultured in vitro (11 human tumor types with 3 to 24 tumors each: bladder, colon, gastric, NSCLC, SCLC, breast, ovary, pancreatic, renal, melanoma, and pleuramesothelioma). Everolimus inhibited colony formation in a concentration-dependent manner (mean IC₅₀: 175 nM). In addition, normal hematopoietic stem cells were found to be relatively insensitive to everolimus, with an IC₅₀ about 15 fold higher than the tumor lines.

Everolimus was effective and well tolerated against subcutaneous (s.c.) tumors established from a variety of tumor cell lines of diverse histotypes (NSCLC, pancreatic, colon, melanoma, epidermoid), including a PgP170-overexpressing, multi-drug resistant tumor line. Typically, the antitumor activity of everolimus was that of reduction of tumor growth rates rather than producing regressions or stable disease although, in the case of A549 and NCI-H596 lung and ARJ42 pancreatic tumors, regressions could be obtained. These effects occurred within the dose range of 2.5 to 10 mg/kg, p.o., once per day. The change in tumor volume of the treated mice divided by the change in tumor volume of control mice (T/C) typically ranged from approximately 15 to 50% at optimal doses. A marked loss of antitumor activity occurred when tumor-bearing mice were treated with everolimus once per week, but improved moderately

with twice per week dosing. Antitumor activity of everolimus has also been demonstrated in mouse models of ovarian (Mabuchi, et al 2007), breast (Lu, et al 2007, Torres-Arzayus, et al 2007) and gastrointestinal stromal tumors (Rossi, et al 2006).

Pre-clinical safety

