1.4 Rationale

We have shown that methylation of the PTEN promoter occurs frequently in low-grade gliomas and secondary glioblastomas, and is associated with PI3K signaling and PKB/Akt phosphorylation (Wiencke et al. 2007). Given these findings, and the link between (mTOR) and the (PI3K) / PTEN-AKT survival pathway, we hope that RAD001 will also prove efficacious in the treatment of low-grade gliomas and secondary malignant gliomas as delineated in the study proposed herein.

In this study, molecular features, including PTEN status and PKB/Akt phosphorylation will be assessed prospectively in this trial to test the hypothesis that those tumors with PTEN methylation and consequent PKB/Akt phosphorylation will preferentially respond to mTOR inhibition.

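### The p-Akt testing question is read from an odds ratio alone: no response rate by marker status is planned, and the usual estimators fail if no marker-negative tumour responds

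*Combined protocol and SAP*

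**What the plan says.** Section 6.1.4, under biologic correlates, relates p-Akt status to objective response with a Cochran-Mantel-Haenszel (CMH) test stratified by grade. Logistic regression adjusting for grade is added if responses are sufficient in number, a condition left undefined. The result is then given a purpose, with p-Akt as the marker to be assessed: "Estimates of the odds ratio and its associated 95% confidence interval will be calculated to determine if future studies of RAD001 should require prior assessment". No odds ratio threshold, interval method or rule for an empty cell is stated. The same methods are applied to progression status at 6 months, and the analyses are repeated for PTEN promoter methylation.

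For response itself, the same section says: "The point estimate and the associated 2-sided 95% CI for the response rate will be calculated separately for low grade and secondary malignant tumors". No corresponding estimate by marker status is planned.

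The biological hypothesis, in section 1.4, is that "those tumors with PTEN methylation and consequent PKB/Akt phosphorylation will preferentially respond to mTOR inhibition".

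**The concern.** Whether a later trial should test for p-Akt before enrolment depends largely on how often marker-negative tumours respond. An odds ratio compares the two groups but does not give either rate. As written, the plan ties the question to the relative measure and never commits to estimating the absolute one.

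There is also a computational weakness. With few marker-negative patients and possibly few responses, the marker-negative group may have no responders at all. The standard estimators of the odds ratio then break down. This would happen when the data lean most strongly towards selection by marker, and the plan does not say what would be reported.

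**Working it through.** **Inputs.** Section 6.1.3 (Estimated Duration of Study): "we should be able to complete enrollment of 40 low-grade glioma patients and 20" secondary malignant glioma patients. Section 6.1.4: "We also expect approximately 50% of the low-grade tumors to be phosphorylated PKB/Akt positive" and "75% of the higher-grade tumors to be positive". The documents give no expected response rate, so every response rate below is an assumption.

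**1. The plan's counts.** 40 × 0.50 = 20 and 20 × 0.75 = 15, which reproduces the stated 20 and 15 positive cases. Positives: 20 + 15 = 35. Negatives: 20 + 5 = 25.

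**2. One odds ratio, different absolute rates.**
- 30% versus 12.5%: (0.30/0.70) / (0.125/0.875) = 3.0
- 6% versus 2%: (0.06/0.94) / (0.02/0.98) = 3.1

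In the first case one marker-negative patient in eight responds; in the second, almost nobody responds in either group.

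**3. Empty marker-negative cell.** Take as illustration 4/20 and 3/15 positive responders, with 0/20 and 0/5 among negatives.
- Mantel-Haenszel odds ratio = Σ(a·d/n) / Σ(b·c/n), where a and b are positive responders and non-responders, and c and d the same for negatives. Numerator: 4·20/40 + 3·5/20 = 2.75. Denominator: 16·0/40 + 12·0/20 = 0. The ratio is infinite.
- Maximum-likelihood logistic regression with grade separates: log odds ratio about 22.2, standard error about 15,900. The Wald interval carries no information.
- CMH test: observed 7, expected 2 + 2.25 = 4.25, variance 0.923 + 0.503 = 1.426. Chi-square = 2.75²/1.426 = 5.30, p = 0.021 uncorrected (0.060 with continuity correction). It remains computable.
- Exact conditional: one-sided p = [C(20,4)/C(40,4)] × [C(15,3)/C(20,3)] = 0.0530 × 0.399 = 0.021, doubled 0.042. The 95% interval for the odds ratio is 1.06 to infinity. With 6/20 and 5/15 positive responders its lower limit is 2.05.
- Firth penalised logistic: odds ratio 13.2, 95% interval 1.4 to about 1,770.

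**4. How likely is it?** P(0/25) = (1 − pₙ)²⁵. An infinite odds ratio also needs a positive responder, so its probability is (1 − pₙ)²⁵ × [1 − (1 − pₚ)³⁵].

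| True rate, negatives | P(0/25) |
|---|---|
| 2% | 60% |
| 5% | 28% |
| 10% | 7% |

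With negatives at 2%, the probability of an infinite odds ratio is 0.603 × (1 − 0.98³⁵) = 31% if positives also respond at 2%, and 0.603 × (1 − 0.94³⁵) = 53% if positives respond at 6%.

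**5. Other endpoint.** For 6-month progression-free status at the plan's 17% lower threshold, P(0/25) = 0.83²⁵ = 0.9%. The empty cell is mainly a response problem.

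**6. What the marker-negative rate would show.** 0/25 has an exact two-sided 95% interval of 0 to 13.7% (upper limit 1 − 0.025^(1/25)). Within grade, 0/20 has an upper limit of 16.8% and 0/5 of 52.2%.

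**7. Sparse p-values.** Four responders, all p-Akt positive low-grade: CMH p = 0.037 uncorrected and 0.118 with continuity correction; exact two-sided p = 2 × 0.0530 = 0.106; exact lower limit for the odds ratio 0.71. The plan does not say which CMH form applies.

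**The case against.** Much can be said for the plan, and several stronger readings fail.

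- *A reader might infer that no responses among marker-negative tumours is what the hypothesis predicts.* Section 1.4 speaks of preferential, not exclusive, response. An empty cell is its strongest form.
- *A reader might infer that the odds ratio interval could not be computed at all.* The plan does not fix an interval method. An exact interval has an informative finite lower limit, a Firth interval is finite, and the CMH test still works. What fails is the Mantel-Haenszel or maximum-likelihood estimate with its Wald-type interval.
- *A reader might apply the 60%, 28% and 7% to an infinite odds ratio whatever the positives do.* With no responder in either group the odds ratio is undefined rather than infinite, so those figures are upper bounds.
- *A reader might take the sparse example as proof that the planned CMH p-value misleads.* It does so only without continuity correction; the corrected value is close to the exact one. The example shows an unstated choice.
- The condition on logistic regression might lead an analyst to drop the model when a cell is empty. That is possible, but with no definition it cannot be relied on: 7/35 versus 0/25 has seven responses and still no finite estimate.
- Low response is not established. Section 1.1.2 says of preclinical models: "Typically, the antitumor activity of everolimus was that of reduction of tumor growth rates rather than producing regressions or stable disease". Yet section 1.1.3.6 reports regression in every treated tuberous sclerosis patient with low-grade glioma. Neither gives a response rate for this population.
- A grade-stratified CMH test needs the response-by-marker counts, so an analyst would have them. The plan still does not commit to reporting rates from them or to using them for the testing question.

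The analysis is secondary, in a single-arm phase II trial, and nothing in the conduct of this trial depends on it. That limits the weight of the point without removing it.

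**Conclusion.** The point holds in a limited form. The plan names an odds ratio and its interval as the basis for judging whether future studies should require p-Akt assessment, and it plans no response rate by marker status. The odds ratio alone cannot show whether marker-negative tumours respond at a useful rate; this is the firmer half and needs no empty cell. The second half is conditional: with 0/25 negative responders and at least one positive responder, the usual odds ratio estimates are infinite and their Wald-type intervals unusable. The size of that risk rests on assumed response rates and on the plan's expected 35/25 split. It is substantial only if negatives respond at about 5% or less, and it is improbable for 6-month progression status. The documents do not support the view that the planned analysis cannot be carried out. Severity: minor.

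**What to change.** In section 6.1.4, under biologic correlates:

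1. Report response counts, rates and exact 95% intervals in marker-positive and marker-negative patients, overall and within grade. State that the question of requiring prior assessment will be read from these alongside the odds ratio.
2. When cells are sparse, use exact conditional (or Firth penalised) grade-stratified inference for the odds ratio, its interval and its p-value, in place of large-sample CMH and maximum-likelihood logistic regression.
3. Apply the same to PTEN promoter methylation.

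This changes wording only and needs no new data. The cost is that exact intervals are somewhat wider and exact p-values less favourable than the uncorrected CMH (0.042 versus 0.021 in the 4/20 and 3/15 example). It does not add precision: with 25 negatives, even no responses leaves rates up to 13.7% compatible with the data, and the documents do not say what rate would count as useful.
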